13.0 CORRELATIVE STUDIES

All correlative studies are optional and failure to collect these studies at any of the specified time-points is not a protocol deviation.

Correlative Studies relating to immunologic response will be collected on a separate IRB-approved Protocol (PA13-0291).

Approximately 30cc of peripheral blood will be collected at the following time-points (pretreatment, C1D1,

C1D15, C2D1, C3D1, end of C3, C5D1, C6D1, end of C6, C8D1, C9D1, end of C9, C11D1, C12D1, end of C12, end of C18, end of C24) and stored in the Leukemia Research Bank. Approximately 6cc of bone marrow aspirate will be collected at the following time-points (pretreatment, C2D1 (only for cohort 1), end of C3, end of C6, end of C9, end of C12, end of C18, end of C24) and stored in the Leukemia Research Bank.

Coevolution of tumor and immune cell heterogeneity following combined ibrutinib and nivolumab therapy in CLL ([name], Dana-Farber Cancer Institute, Boston, MA) – We propose a correlative study to analyze both tumor and immune cells in the marrow and peripheral blood microenvironments of CLL, using samples from responders and non-responders, pre- and post-treatment. Using emerging single cell profiling tools to deeply monitor the genetic and molecular processes occurring within tumors from patients undergoing immune modulation, we hope to derive the co-evolutionary trajectories and principles that underlie the success or failure of immunomodulatory therapy. The protocol for freezing whole blood and marrow aspirate is in Appendix 4. The research methods and design are detailed in Appendix 5.

14.0 STATISTICAL CONSIDERATIONS

EFFICACY

A maximum of 72 patients will be enrolled in this Phase II study. Cohort 1 and 3 will enroll up to 24 patients each who were refractory to or relapsed after at least one prior standard therapy or untreated with del(17p) by FISH; Cohort 2 will enroll up to 24 patients who have been on ibrutinib for at least 9 months and have achieved a partial response.

Note: Statistical analysis and stopping rules, and toxicity assessment for Cohort 3 will be same as Cohort 1.

In the first cohort, the primary objective is to evaluate best response during the first 12-month of therapy. The primary efficacy endpoint, best response (BR), is defined as CR or CRi that occurs during the first 12 months of treatment. The optimum two-stage design proposed by Simon will be implemented.⁵⁶ We assume a target BR rate of 20% and a BR rate of 5% or lower will be considered not desirable. With a type I error rate of 10% and 80% power, we will enroll 9 patients in the first stage. If no patients achieve BR, the trial will be stopped. If 1 or more out of the first 9 patients have BR, accrual will continue until a total of 24 patients have been enrolled. We will suspend accrual at the end of the first stage, if all 9 patients have been enrolled, yet no responder (CR or CRi) has been observed. At the end of the study, if 3 or more out of the 24 patients achieve BR, the combination treatment will be considered efficacious and is worth further investigation. Under this Simon's two-stage design, the probability of early termination is 63% if the true BR is 5% and the expected sample size is 14.6 patients.

In the second cohort, the primary objective is to evaluate conversion rate during the first 12-month of therapy. The primary efficacy endpoint, conversion rate is defined as the conversion from partial response (PR) to complete response (CR/CRi) that occurs during the first 12 months of treatment. Up to 24 patients will be enrolled in this cohort. The same Simon's optimum two-stage design as described above will be used here in cohort 2. We assume a target conversion rate of 20% and a conversion rate of 5% or lower will be considered not desirable. With a type I error rate of 10% and 80% power, we will enroll 9 patients in the first stage. If no patient converts from PR to CR, the trial will be stopped. If 1 or more out of the first

9 patients achieve conversion, accrual will continue until a total of 24 patients have been enrolled. We will suspend accrual at the end of the first stage, if all 9 patients have been enrolled, yet no conversion has been observed. At the end of the study, if 3 or more out of the 24 patients achieve conversion, the combination treatment will be considered efficacious and is worth further investigation. Under this design, the probability of early termination is 63% if the true conversion rate is 5% and the expected sample size is 14.6 patients.

TOXICITY

The Bayesian approach of Thall, Simon, Estey will be implemented for toxicity monitoring for patients enrolled in cohorts 1 and 2, where toxicity is defined as any grade 3 or higher non-hematological toxicity which is at least possibly related to the treatment.⁵⁷ The toxicity, denoted as TOX will be monitored by the Bayesian stopping boundaries calculated based on beta-binomial distributions. We assume as a priori, $p(\text{TOX}) \sim \text{beta}(0.6, 1.4)$. The study will be stopped for toxicity if $\text{Pr}(p(\text{TOX}) > 0.30 | \text{data}) > 0.8$. That is, we will stop the trial for new patient enrollment if at any time during the study we determine that there is more than 80% chance that the toxicity rate is more than 30%. The toxicity monitoring rule will be applied starting from the 6th patient, and then in cohort size of 6. The toxicity will be considered continuously throughout the study treatment duration. Stopping boundaries corresponding to this toxicity monitoring rule are shown in Table 14.1 below. The operating characteristics for toxicity monitoring are summarized in Table 14.2.

Table 14.1. Toxicity stopping boundaries in cohort size of 6 for patients enrolled in cohorts 1 and 2.

Number of patients	Stop the trial if there are this many patients having toxicity
6	3-6
12	6-12
18	8-18
24	10-24
30	12-30
36	14-36
42	16-42

Table 14.2. Operating characteristics for toxicity monitoring.

True Toxicity Rate	Early Stopping Probability	Average number of patients treated
0.1	0.02	47.3
0.2	0.12	43.4
0.3	0.41	33.8
0.4	0.81	20.7
0.5	0.98	11.7

ANALYSIS PLAN

Summary statistics will be provided for continuous variables. Frequency tables will be used to summarize categorical variables. The best response rate for cohort 1 and conversion rate for cohort 2 will be estimated along with the exact 95% confidence interval.

Data from all patients who receive any study drug will be included in the safety analyses. Patients who entered the study and did not take any of the study drugs and had this confirmed will not be evaluated for safety. The severity of the toxicities will be graded according to the NCI CTCAE v4.0 whenever possible. We will follow standard reporting guidelines for adverse events. Safety data will be summarized by category, severity and frequency. The proportion of patients with AEs will be estimated, along with the Bayesian 95% credible interval. Kaplan-Meier method will be used to assess the overall survival (OS) and progression-free survival (PFS) probabilities. The change of biomarkers over time will be assessed through fitting linear or non-linear mixed effect models.

This study will be conducted as described in this protocol, except for an emergency situation in which the protection, safety, and wellbeing of the patient requires immediate intervention, based on the judgment of the investigator or his/her designee. In the event of a significant deviation from the protocol, the investigator will notify the MDACC surveillance committee following the institutional guidelines.

Statistical Language for the correlative studies: Descriptive statistics including plots, mean, median and standard deviations will be used to summarize data. For continuous outcomes, t-test and ANOVA will be used to compare outcome measures across patient characteristics. Dunnett's and Tukey's test that properly adjust for multiplicity in multiple tests will be implemented. Pair-wise comparisons will be performed using pre- and post-therapy samples from each patient. The chi-square (c2) test or Fisher's exact test will be used to test the association between two categorical variables such as disease state and performance status. Both univariate and multivariate logistic regressions will be performed to model prognostic factors.

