1.0 OBJECTIVES

Primary Objectives

1. To determine the efficacy (response rate) of nivolumab in combination with ibrutinib in patients with relapsed/refractory or high-risk untreated CLL by
 - a. Cohort 1: determine the response rate (CR/CRi) by 2008 IWCLL criteria
 - b. Cohort 2: determine the conversion rate from PR to CR/CRi by 2008 IWCLL criteria
 - c. Cohort 3: determine the response rate (CR/CRi)

Secondary Objectives

1. To determine the safety of nivolumab in combination with ibrutinib in patients with relapsed, refractory or high-risk untreated CLL/Richter transformation (RT).
2. To determine the progression-free survival of patients with relapsed, refractory or high-risk untreated CLL/RT treated with nivolumab in combination with ibrutinib.
3. To determine the overall survival of patients with relapsed, refractory or high-risk untreated CLL/RT treated with nivolumab in combination with ibrutinib.

Exploratory Objectives

1. To study immunological and molecular changes in peripheral blood, lymph node, and bone marrow in response to nivolumab and ibrutinib therapy.

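### The Cohort 2 stage-1 stop sentence omits CRi, so a first stage with only CRi conversions meets both the stop rule and the continue rule

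*Combined protocol and SAP*

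**What the plan says.** Section 1.0 gives the objective as "Cohort 2: determine the conversion rate from PR to CR/CRi by 2008 IWCLL criteria". Section 14.0 repeats the composite: "conversion rate is defined as the conversion from partial response (PR) to complete response (CR/CRi) that occurs during the first 12 months of treatment". The design is taken over from Cohort 1: "The same Simon's optimum two-stage design as described above will be used here in cohort 2". Its parameters are set on the conversion rate: "We assume a target conversion rate of 20% and a conversion rate of 5% or lower will be considered not desirable", and "With a type I error rate of 10% and 80% power, we will enroll 9 patients in the first stage".

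Four Cohort 2 decision rules follow in Section 14.0:

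- Stop: "If no patient converts from PR to CR, the trial will be stopped".
- Continue to 24 patients if at least 1 of the first 9 achieves conversion.
- Suspend accrual if all 9 are enrolled and no conversion has been seen.
- Declare the combination worth pursuing if at least 3 of 24 achieve conversion.

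Only the first names CR alone. In Cohort 1 the stop, continue and final rules count best response, defined as CR or CRi, and the suspension rule spells it out: "yet no responder (CR or CRi) has been observed". Cohort 3 follows Cohort 1, so neither of those cohorts is affected.

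**The concern.** The stop and continue sentences should be complements, but as written they overlap. If the first nine patients include at least one CRi conversion and no CR, the stop sentence closes enrolment and the next sentence takes it to 24. This is a binding decision rule, and response is assessed by the investigator in an open-label study (Sections 4.1 and 10.0). If the conflict is found only when such a first stage occurs, it will be settled with the results known, and either choice would be post hoc. The literal stop reading would also end a cohort in which the defined endpoint had been observed, which lowers power by an amount that depends on how common CRi is.

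**Working it through.** **Inputs.** From Section 14.0: p0 = 0.05, p1 = 0.20, first stage 9, total 24, continue with at least 1 conversion, success with at least 3. The CRi share of conversions, s, is not in the documents and is varied as an assumption.

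**Step 1: reproduce the plan, counting CR/CRi throughout.**

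Early termination at 5% = 0.95^9 = 0.630 (stated 63%).

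Expected sample size at 5% = 9 + 15 × (1 − 0.630) = 14.55 (stated 14.6).

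P(success) = Σ over x = 1 to 9 of P(X = x) × P(Y ≥ 3 − x), with X ~ Bin(9, p) and Y ~ Bin(15, p).

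- At p = 0.20: 0.3020 × 0.8329 + 0.3020 × 0.9648 + 0.2618 = 0.2515 + 0.2914 + 0.2618 = 0.805 (stated power 80%).
- At p = 0.05: 0.2985 × 0.1710 + 0.0629 × 0.5367 + 0.0084 = 0.0510 + 0.0337 + 0.0084 = 0.093 (stated limit 10%).

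A search over total sample sizes up to 40 with these error limits returns the same optimal design: 0 of 9, then 3 of 24.

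**Step 2: apply the stop sentence literally.** Each conversion is independently a CRi with probability s. Stage 1 continues only if at least one conversion is a CR. The final rule still counts CR and CRi.

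- Stage-1 stop = (1 − p(1 − s))^9
- Chance that both rules are met = (1 − p(1 − s))^9 − (1 − p)^9
- Power = Σ over x of P(X = x) × (1 − s^x) × P(Y ≥ 3 − x)

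Example at p = 0.20, s = 0.25:

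- Stop = 0.85^9 = 0.2316.
- Both rules met = 0.2316 − 0.1342 = 0.0974.
- Power = 0.75 × 0.2515 + 0.9375 × 0.2914 + 0.2588 = 0.721, where 0.2588 is the 0.2618 for x ≥ 3 less the 0.0030 in which all those conversions are CRi.

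| Assumed CRi share | Stage-1 stop at 20% | Both rules met at 20% | Power at 20% | Early termination at 5% |
|---|---|---|---|---|
| 0% | 13.4% | 0% | 80.5% | 63.0% |
| 5% | 15.0% | 1.6% | 79.1% | 64.5% |
| 10% | 16.8% | 3.3% | 77.6% | 66.1% |
| 25% | 23.2% | 9.7% | 72.1% | 70.9% |
| 33% | 27.4% | 14.0% | 68.3% | 73.6% |
| 50% | 38.7% | 25.3% | 57.9% | 79.6% |

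Power falls below 80% once the share exceeds about 1.8%, and below 78% once it exceeds about 8.9%. At a 50% share and a true 5% rate, the expected sample size is 12.1 and the type I error 5.8%, so the literal reading does not inflate false positives.

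**Step 3: compare the text on CRi.** Section 10.0 first attaches CRi to a hypocellular marrow, under the CR criteria. It then lists, among patients otherwise meeting CR who are to be considered a PR, those with persistent cytopenia probably due to drug toxicity, and says that these too may be noted as CRi. Cohort 2 patients start in PR, so under the second entry a patient noted as CRi may not have converted at all.

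**The case against.** The strongest reply is that CR here is shorthand. The endpoint sentence in the same paragraph glosses complete response as CR/CRi, the objective says the same, and the design is declared identical to that of Cohort 1. The continue, suspension and final rules all use conversion, and the stated 63% and 14.6 are expressed on the conversion rate. In a first stage with only CRi conversions, the suspension rule would not be triggered either. All of this stands, and it settles the intent.

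A reader might infer that Cohort 2 does not have its stated 80% power, or that its design figures are wrong. The documents do not support that. The figures reproduce on the defined endpoint. A loss arises only if the one outlying sentence overrides all the others and CRi is a material share of conversions. The documents give no share, and below about 9% the fall from the stated 80% is under 2 percentage points.

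The reply does not remove the overlap. Section 10.0 uses CR and CRi as separate labels and places some CRi patients under PR, so the literal reading has some textual support.

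**Conclusion.** The point holds as a wording inconsistency in a binding stopping rule. The Cohort 2 design, boundaries and stated operating characteristics are correct for the CR/CRi endpoint; the stop sentence alone does not match them. Literal use at a true 20% rate would give power from 79% (CRi share 5%) to 58% (share 50%), with a 1.6% to 25% chance of a first stage that meets both rules. Those figures assume that each conversion is independently a CRi with the same probability, that the final rule counts CR and CRi, and that the CRi share lies in a range chosen for illustration. They show what the ambiguity could cost if it were resolved the wrong way, not the performance of the design as intended.

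**What to change.** Change the Cohort 2 stop sentence to: *If no patient among the first 9 converts from PR to CR or CRi, the trial will be stopped.* This leaves the scope of the stop as it is now. State that the same CR/CRi count applies to the continue, suspension and final 3-of-24 rules. In the same amendment, reconcile the Section 10.0 entry that places some patients noted as CRi under PR with the Cohort 2 endpoint, so that it is clear which CRi outcomes count as conversions. The Section 14.0 edit is one phrase and changes no sample size, boundary or stated figure. The Section 10.0 clarification is short but needs a decision by the investigators on response classification, best made before any Cohort 2 first-stage result is reviewed.

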APPENDIX 1: SAMPLE OF DRUG ORDERING AND PHARMACY REFERENCE MATERIAL

Nivolumab (BMS-936558) Pharmacy Reference Material

- Nivolumab has a concentration of 10mg/mL and is provided in a 10mL vial. Ten or five vials are provided in a carton.

Initial Orders

- *Following submission and approval of the required regulatory documents, a supply of nivolumab may be ordered from by completing a Drug Request Form provided by BMS for this specific trial. The first request may take place upon screening of the first patient*
- *The initial order should be limited to 20 vials. Allow 5 business days for shipment of drug from BMS receipt of the Drug Request Form. Drug is protocol specific, but not patient specific. All drug product will be shipped by courier in a temperature-controlled container. It is possible that sites may have more than one nivolumab clinical study ongoing at the same time. It is imperative that only drug product designated for this protocol number be used for this study.*
- Pharmacy supplies not provided by BMS: Empty IV bags/containers, approved diluents, In-line filters and infusion tubing

Re-Supply

- *Drug re-supply request form should be submitted electronically business days before the expected delivery date. Deliveries will be made Tuesday through Friday.*
- *When assessing need for resupply, institutions should keep in mind the number of vials used per treatment dose, and that shipments may take 14 business days from receipt of request. Drug is not patient-specific. Be sure to check with your pharmacy regarding existing investigational stock to assure optimal use of drug on hand.*

Drug Excursions

- *Drug excursions should be reported immediately to BMS on the form provided with the study-specific drug order form*

Please refer to the most recent version of the Investigator Brochure for additional information.
Storage Conditions & Handling:

- Store at 2-8°C (36-46°F), protect from light, freezing, and shaking.
- If any temperature excursions are encountered during storage, please report these to BMS for assessment via the Temperature Excursion Response Form.
- As with all injectable drugs, care should be taken when handling and preparing nivolumab. Whenever possible, nivolumab should be prepared in a laminar flow hood or safety cabinet using standard precautions for the safe handling of intravenous agents applying aseptic technique.
- Partially used vials should be disposed at the site following procedures for the disposal of anticancer drugs.

After final drug reconciliation, unused nivolumab vials should be disposed at the site following procedures for the disposal of anticancer drugs. For further information, please either discuss with your BMS CSR&O protocol manager or refer to your site IP Destruction policies and procedures

Use Time/Stability: Please refer to section 3.2.3 of the current Investigator Brochure. Due to parameters surrounding the use time of Nivolumab, the time of preparation should be noted in the Pharmacy Source documents [accountability logs] or in study files as required for investigator sponsored research [FDA and GCP]

The administration of BMS-936558-01 injection prepared for dosing nivolumab infusion must be completed within 24 hours of preparation. If not used immediately, the infusion solution may be stored up to 20 hours in a refrigerator at under refrigeration conditions (2°-8°C, 36°-46°F) and used within 4 for up to 24 hours, and a maximum of 4 hours of the total 24 hours can be at room temperature (20°-25°C, 68°-77°F) and under room light. The maximum 4-hour period under room temperature and room light conditions for undiluted and diluted solutions of BMS-936558-01 injection in the IV bag should be inclusive of the includes the product administration period.

Preparation and Administration:

1. Visually inspect the drug product solution for particulate matter and discoloration prior to administration. Discard if solution is cloudy, if there is pronounced discoloration (solution may have a pale-yellow color), or if there is foreign particulate matter other than a few translucent-to-white, amorphous particles.
*Note: Mix by **gently** inverting several times. **Do not** shake.*
2. Aseptically withdraw the required volume of nivolumab solution into a syringe, and dispense into an IV. bag. If multiple vials are needed for a subject, it is important to use a separate sterile syringe and needle for each vial to prevent problems such as dulling of needle tip, stopper coring, repeated friction of plunger against syringe barrel wall. **Do not** enter into each vial more than once. **Do not** administer study drug as an IV push or bolus injection
3. Add the appropriate volume of 0.9% Sodium Chloride Injection solution or 5% Dextrose Injection solution. *It is acceptable to add nivolumab solution from the vials into an appropriate pre-filled bag of diluent.*

Note: Nivolumab infusion concentration must be at or above the minimum allowable concentration of 1 mg/mL.

Note: It is not recommended that so-called “channel” or tube systems are used to transport prepared infusions of nivolumab.

4. Attach the IV bag containing the nivolumab solution to the infusion set and filter.
5. At the end of the infusion period, flush the line with a sufficient quantity of approved diluents.

Example Dose Calculation [at 3mg/kg]

Total dose should be calculated as follows (assuming total dose volume of 210 mL, 70 kg pt, dose of 3 mg/kg):

- Subject body weight in kg x 3 mg (for the 3 mg/kg cohort) = total dose (mg)
 $70 \text{ kg} \times 3 \text{ mg/kg} = 210 \text{ mg}$
- Total dose (mg) \div 10 mg/mL = Amount of solution to be withdrawn from vials
 $210 \text{ mg} \div 10 \text{ mg/mL} = 21 \text{ mL}$

Example of Total volume of solution to infuse (mL) for a minimum conc solution. – Volume of 10 mg/mL solution (mL) = Volume of Diluent (mL) to add

$$210 \text{ mL} - 21 \text{ mL} = 189 \text{ mL}$$

Please note it is perfectly acceptable to dose Nivolumab at a higher drug concentrations, **as long as the total volume of diluted solution is at or above the minimum allowable concentration of 1 mg/mL, below is the calculation based on the above example. Please double check.**

Total dose in mg \div Total volume to infuse in mL = Overall drug concentration, mg/mL

$$210 \text{ mg} \div 210 \text{ mL} = 1 \text{ mg/mL}$$

Appendix 2: Inhibitors and Inducers of CYP3A4/5

Inhibitors of CYP3A4/5 are defined as follows. A comprehensive list of inhibitors can be found at the following website: <http://medicine.iupui.edu/clinpharm/ddis/table.aspx>. The general categorization into strong, moderate, and weak inhibitors according to the website is displayed below. Refer to Section 6.2 on instructions for concomitant use of CYP3A4/5 inhibitors or inducers with ibrutinib.

Inhibitors of CYP3A4/5	Inducers of CYP3A4/5
Strong inhibitors: INDINAVIR NELFINAVIR RITONAVIR CLARITHROMYCIN ITRACONAZOLE KETOCONAZOLE NEFAZODONE SAQUINAVIR SUBOXONE TELITHROMYCIN	Carbamazepine Efavirenz Nevirapine Barbiturates Glucocorticoids Modafinil Oxcarbazepine Phenobarbital Phenytoin Pioglitazone Rifabutin Rifampin St. John's Wort Troglitazone
Moderate inhibitors: aprepitant erythromycin diltiazem fluconazole grapefruit juice Seville orange juice verapamil	
Weak inhibitors: cimetidine	
All other inhibitors: amiodarone NOT azithromycin chloramphenicol boceprevir ciprofloxacin delavirdine	
fluvoxamine gestodene mibepradil mifepristone norfloxacin norfluoxetine star fruit telaprevir voriconazole	

Source: <http://medicine.iupui.edu/clinpharm/ddis/table.aspx>

